5 STATISTICAL ANALYSES

5.1 Sample size

Sample size has been calculated using the graphical method for 2x2 factorial designs informed by the Fleiss equation, described by Byth and Gebski (71). Making a conservative assumption of sub-additive interaction between the 2 interventions (interaction coefficient of 0.5), then at a level of significance of 5%, a sample size of 444 (111 participants in each arm) will provide 82% power to demonstrate that each treatment results in a 20% reduction in the proportion culture positive at one month (from 60% to 40%), assuming loss to follow up of 10%. As there have been no trials of co-administration of vitamin D and L-arginine, the characteristics of potential immunological interactions can be extrapolated only from in vitro macrophage studies, in which findings conflict: vitamin D was found to inhibit iNOS expression in one study(44); yet upregulate NOS2A in another (68); the latter study also found the suppressive effect of vitamin D on MTB replication to be partially impaired if NO formation was inhibited. Including a sub-additive interaction term in the sample size calculation provides a margin a caution; if there is minimal or no interaction between the two interventions, our power will be greater. A factorial design rather than a three-arm study allows us to investigate whether if is safe and effective to co-administer the two interventions. Acknowledging the possibility of statistical interaction between the terms, we have an *a priori* plan to analyse primary and secondary outcomes according to subgroups receiving single interventions as well as according to the overall factorial model (71).

Mean time to culture negativity in mostly drug sensitive TB is 32 days (New York) (72) -57 days (Turkey) (73). Based on bacillary burden and extent of cavitatory disease, we estimate a minimum of 60% of Timika patients will be culture positive at 1 month. Our power will be increased if this proportion is higher. This sample size will also be powered to detect a 9% absolute difference in the mean improvement in percent predicted FEV1, a component of the composite endpoint, at 6 months. Mean baseline percent predicted FEV1 in Timika is 63.6% predicted (SD 22) rising to 77.9% predicted (SD 23) at 6 months. Each month, at least 25 eligible smear positive pulmonary TB patients are diagnosed and treated at the Timika study site. If 90% agree to be enrolled, recruitment will take <2yrs to complete.

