4 TRIAL OUTCOME MEASURES

4.1 Primary outcome measures

- 1. Proportion of pulmonary TB patients who are culture negative at 1 month
- 2. Difference in improvement in composite clinical endpoint comprising weight, cough clearance and FEV_1 at 2 months.

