4.2 Secondary outcome measures

- 1. Safety.
- 2. Difference in improvement in percent predicted FEV_1 at 2 and 6 months.
- 3. Change in plasma L-arginine and 25(OH)D₃ concentrations.
- 4. Weight gain.
- 5. Cough clearance.

- 6. Sputum smear conversion time.
- 7. Functional improvement including Six minute walk test and quality of life assessment using modified St George Respiratory Questionnaire.
- 8. Immunological improvement (exhaled NO, T cell CD3ζ expression and T cell function).
- 9. Radiological improvement (percentage lung involvement on CXR at 2 months).
- 10. Percentage obstructive and/or restrictive lung disease at 6 months.
- 11. Death, clinical failure and default independently, and 'death or clinical failure or default'.
- 12. Primary end points stratified by HIV status.
- 13. Primary end points stratified by baseline vitamin D and L-arginine status.
- 14. Primary end points stratified by ethnicity (Papuan and non-Papuan patients).

Use of mycobacterial culture as a primary outcome measure overcomes the potential problem of continued smear positivity of non-viable organisms. Culture at one month will capture any early microbiological effect of adjuvant therapy. As we have shown in previous work in Timika, FEV_1 at 2 months is predictive of longer term deficits in lung function that may be modified by early adjuvant therapy. We will also determine the relationship between baseline and serial measurements of pulmonary NO production, serum L-arginine and 25(OH)D₃ concentrations, and clinical, radiological, microbiological and functional measures of disease severity.

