5.2 Outcome Analysis

The primary analysis of all outcomes will be by intention to treat. All participants in the study will contribute outcomes for analysis whenever possible. Each participant's success or failure for the primary outcome will be determined by an independent observer who will be blinded to the intervention. Analyses will use Intercooled Stata 9.2 (Stata Corp, College Station, Texas, USA). 95% confidence intervals and/or p values <0.05 will be employed to signify statistical significance.

As per recent clinical journal requirements, ADAPT will be registered with the protocol registration system at Clinicaltrials.gov.

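### The only lung-function power figure is for FEV1 alone at 6 months, so it does not support the 2-month composite primary outcome, and its basis is not stated

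*Protocol*

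**What the plan says.** The protocol sizes the trial on culture at one month. In section 5.1, 444 patients (111 per arm, 10% loss, sub-additive interaction coefficient 0.5, 5% significance) "will provide 82% power to demonstrate that each treatment results in a 20% reduction in the proportion culture positive at one month". The same section then says the sample size can "detect a 9% absolute difference in the mean improvement in percent predicted FEV1, a component of the composite endpoint, at 6 months", and supports this with "Mean baseline percent predicted FEV1 in Timika is 63.6% predicted (SD 22) rising to 77.9% predicted (SD 23) at 6 months". No other lung-function power statement appears.

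The outcomes are defined as follows.

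- Section 4.1, second primary outcome: "Difference in improvement in composite clinical endpoint comprising weight, cough clearance and" FEV1, at 2 months. The Executive Summary also places the primary lung-function measure at 2 months.
- Section 4.2, item 2 (secondary): "Difference in improvement in percent predicted" FEV1 at 2 and 6 months. The closing paragraph of 4.2 justifies the 2-month visit by its value in predicting later lung-function deficits.

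Section 5.1 also commits in advance to two analyses of the primary and secondary outcomes: by single-intervention subgroups and by the overall factorial model.

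**The concern.** By calling FEV1 a component of the composite, the sentence invites the reader to take it as power for the second primary outcome. It concerns a different variable (one component of three) and a different visit (6 months, not 2).

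It also cannot be checked as written. It speaks of a difference in mean improvement, which is a change score. The SD of a change depends on the correlation between baseline and follow-up, and only the two cross-sectional SDs are printed. Nor does it say whether the comparison is one arm against one arm or a factorial margin of twice that size, or what power is meant.

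At stake is the reading of a null lung-function result. Without a stated comparison, power and SD, nobody can say which FEV1 effects the trial was built to detect, and for the 2-month composite nothing is stated at all.

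**Working it through.** **Inputs.** From section 5.1: 111 per arm, 10% loss, so 111 × 0.9 = 99.9, about 100 evaluable per arm and 200 per factorial margin. SD 22 at baseline and 23 at 6 months. Interaction coefficient 0.5. Assumptions: a two-sided 5% test, because section 5.2 uses 95% intervals and p < 0.05; 80 to 82% power, because 82% is stated only for culture; and baseline-to-follow-up correlation r from 0 to 0.8.

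**Formula.** Detectable difference = (z for alpha + z for power) × SD × √(2/n). The multiplier is 1.960 + 0.842 = 2.802 at 80% power and 2.875 at 82%.

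**Reproducing the 9 points.** Three readings reach about 9.

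1. Single arms, 100 v 100, 80% power: 2.802 × 22 × √(2/100) = 8.7, and 9.1 with SD 23. Power for exactly 9 points is 82.5% (SD 22), 80.7% (SD 22.5) and 79.0% (SD 23).
2. Factorial margins, 200 v 200, with the interaction. I read the coefficient as the second drug adding half of its stand-alone effect; the protocol does not give the scale. The marginal effect is then (1 + 0.5)/2 = 0.75 of the single-drug effect. At 80% power, 2.802 × 22 × √(2/200) / 0.75 = 8.2, and 8.6 with SD 23. At 82% power with SD 23, 2.875 × 23 × 0.1 / 0.75 = 8.8. Equivalently, a 9-point single-drug effect becomes 6.75 on the margin, with power 83.5 to 86.6%.
3. Factorial margins, no interaction, change score with r = 0: SD of change = √(22² + 23²) = 31.8, giving 2.802 × 31.8 × 0.1 = 8.9.

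**A reading that does not give 9.** Factorial margins, no interaction, SD 22 to 23: 6.2 to 6.4 points at 80% power. Power for 9 points is then 97 to 98%.

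**Dependence on the missing correlation.** SD of change = √(22² + 23² − 2r × 22 × 23). This is 31.8 at r = 0, 22.5 at r = 0.5, 17.5 at r = 0.7 and 14.3 at r = 0.8. Single-arm power for 9 points runs from 52% (r = 0) to 99% (r = 0.8). At r = 0.5 the SD of change lies between the two printed SDs, so a change-score calculation and a cross-sectional one cannot be told apart from the stated result.

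**Baseline adjustment.** The ANCOVA residual SD is 23 × √(1 − r²). The last three columns give the detectable difference in points at 80% power.

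| r | SD of change | ANCOVA SD | Variance saved | Margin, no interaction | Margin, 0.5 interaction | Single arms |
|---|---|---|---|---|---|---|
| 0.5 | 22.5 | 19.9 | 22% | 5.6 | 7.4 | 7.9 |
| 0.7 | 17.5 | 16.4 | 11% | 4.6 | 6.1 | 6.5 |
| 0.8 | 14.3 | 13.8 | 6% | 3.9 | 5.2 | 5.5 |

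Variance saved is 1 − (ANCOVA SD / SD of change)²; at r = 0.5, 1 − 396.75/507 = 22%. The interaction column is the no-interaction column divided by 0.75, and the single-arm column is the no-interaction column times √2. Applying the table to week 8 assumes an SD of 23 there, since no 2-month SD is printed.

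**The composite.** No power can be computed for it. The protocol gives no effect size or SD for it, and no 2-month FEV1 figures.

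**The case against.** A reader might infer that 9 points is a single-arm figure and is therefore wrong for a factorial trial. The documents do not support this. The protocol's own 0.5 interaction brings the factorial margin to 8.2 to 8.8, and an uncorrelated change score brings it to 8.9. Single-intervention comparisons are themselves planned in section 5.1, so a single-arm figure would still answer a planned test. For margins without interaction, 9 points is conservative. All of this stands.

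A reader might also infer that cross-sectional SDs were misused for a change score. That cannot be shown either, because r = 0.5 gives the same SD.

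A third inference is that 9 points is implausibly large, being 63% of the whole 6-month gain (77.9 − 63.6 = 14.3; 9/14.3). The protocol offers no benchmark for a plausible FEV1 effect, and 77.9 + 9 = 86.9% predicted is not impossible. The inference should not be drawn.

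Finally, it can be said that a difference in improvement names an outcome rather than a model, and that covariates belong in the analysis plan. That is fair. Baseline adjustment is offered here as a gain in efficiency, not as correction of an error. None of these arguments gives the 2-month composite a power figure or tells the reader which comparison the 9 points refers to.

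**Conclusion.** The point holds in a limited form. The only lung-function power statement concerns one component at 6 months, a secondary outcome, and gives no support to the composite primary outcome at 2 months. Its power, comparison and SD of change are unstated, and several incompatible calculations lead to about 9, so the figure is under-specified rather than wrong.

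The choice of reading matters. With the printed SDs at 80% power, the detectable difference is 6.2 to 6.4 points for margins without interaction and 8.2 to 9.1 for the other two comparisons. Adjusting for baseline would lower each of these by an amount that depends on r. These results assume a two-sided test, 80 to 82% power, the stated 10% loss and, for week 8, an SD of 23. The values of r are assumptions.

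**What to change.** 1. In section 4.2 item 2 and section 5.1, replace the difference in mean improvement in FEV1 by the difference in week-8 and week-24 percent predicted FEV1. Estimate it by ANCOVA adjusting for baseline percent predicted FEV1, place of diagnosis and ethnicity (the two randomisation strata in section 7).
2. In section 5.1, restate the detectable FEV1 difference at week 8. Give the comparison (single arms or factorial margin, with or without the 0.5 interaction), the power, the SD and r. Take the SD and r from the sponsor's own Timika cohort of 115 patients (section 1.3), if its records allow. Label the result as a secondary-outcome figure and say plainly that it does not power the composite.

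The definition of the composite in section 4.1 needs no rewording for this point.

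The cost is an amendment to a few sentences and one short calculation. Appendix 2 already schedules lung function at weeks 0, 8 and 24, and both strata are recorded at enrolment, so no data collection changes.

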5.2 Outcome Analysis

The primary analysis of all outcomes will be by intention to treat. All participants in the study will contribute outcomes for analysis whenever possible. Each participant's success or failure for the primary outcome will be determined by an independent observer who will be blinded to the intervention. Analyses will use Intercooled Stata 9.2 (Stata Corp, College Station, Texas, USA). 95% confidence intervals and/or p values <0.05 will be employed to signify statistical significance.

As per recent clinical journal requirements, ADAPT will be registered with the protocol registration system at Clinicaltrials.gov.

6 ASSESSMENT OF SAFETY

6.1 Intervention Procedure

Potential adverse effects of L-arginine and vitamin D will be carefully monitored. Adverse effects from oral L-arginine are uncommon.(27) Use of up to 21g daily was not associated with adverse events in two studies(28, 74). Oral L-arginine 7g three times daily for 4 weeks was associated with diarrhoea in 3 of 27 patients, but this resolved on dose reduction to 7g twice daily(75). Minor gastrointestinal discomfort has been reported in up to 3% of patients(27, 76). We do not expect that this will be a problem but will monitor our study patients carefully for this adverse effect and treat accordingly.

Although much less common than in other granulomatous diseases, vitamin D supplementation in TB has the potential for hypercalcaemia from extra-renal $1,25(OH)_2D_3$ production(77). Based on our previous experience with vitamin D supplementation ([name], personal communication), and extensive review of the literature(60, 78-81), the risk of symptomatic hypercalcaemia as a complication of vitamin D supplementation at the dose proposed in this study(63) in patients with pulmonary TB is anticipated to be very low. Ionised calcium will be measured, using portable i-STAT cartridges in Timika, at 0, 2, 4 and 8 weeks. In the unlikely event of hypercalcaemia developing, the literature indicates that the most likely time of onset would be 2-4 weeks post commencement of anti-TB therapy. Patients found to have elevated *i*Ca²⁺ on follow up will have their Vit D/placebo dose withheld.

6.2 **TB Medication side effects**

All patients with pulmonary TB in the study will be treated with anti-tuberculous agents according to the standard NTP protocol. This comprises daily weight-adjusted doses of Rifampicin (R), Isoniazid (H), Pyrazinamide (Z) and Ethambutol (E). Medications are taken under direct observation by health care workers during the intensive phase. Treating doctors will comply with NTP guidelines with regards to standard monitoring for TB drug side effects.

6.3 Stopping rules

Adverse events defined as serious will be i) death and ii) ionised hypercalemia >1.6 mmol/L or hypercalcaemia requiring hospitalisation. All serious adverse events (SAE) will be reported to the chair of the DSMC. It is expected that death may occur during the 6 month treatment and follow up period in up to 5% of patients enrolled in the study related to TB itself (eg advanced/disseminated disease) or comorbidities (eg AIDS). An interim analysis will be performed after 25 and 50% of participants have

been followed to 2 months, or as requested by the DSMC in the event of SAE related to study drugs. The DSMC will be able to recommend that enrolment into the study ceases if they believe there is evidence that individuals are being harmed through their participation in the study. Early termination of the study (or of one of the study arms) may also be recommended if there is strong evidence of benefit or harm associated with either of the interventions at the interim analysis (p<0.01) or if there is strong evidence that further enrolment will not provide any useful information.

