Appendix 5: Recognition of Adverse Events

Management of Adverse Events

Definitions

Adverse Event (AE): any untoward medical occurrence in a clinical trial subject administered a pharmaceutical product, not necessarily related to the study drugs or TB drugs. FILL IN ADVERSE EVENTS REPOTING FORM and record on patient's weekly data collection form and medical file. Report to [name] and [name] [name] as per Safety Reporting Flwoshart.

Serious adverse event (SAE): any untoward medical occurrence in a clinical trial subject administered a pharmaceutical product, which is life-threatening, results in death, requires hospitalisation or prolongation of existing hospitalisation, results in significant disability / incapacity or congenital anomaly / birth defect. FILL IN SERIOUS ADVERSE EVENTS REPOTING FORM and record on patient's weekly data collection form and medical file. Report to [name] and [name] [name] as per Safety Reporting Flwoshart.

Potential study drug-related AE

Arginine

- Diarrhoea
- Bloating
- Nausea
- Vomiting
- Mild to moderate abdominal pain
- Urticarial skin rash

Vitamin D

- Asymptomatic hypercalcaemia defined as $iCa^{2+} > 1.32 \text{ mmol/L}$
- Symptomatic hypercalcaemia i.e. $iCa^{2+} > 1.32$ mmol/L with one or more of the following symptoms or signs:
 - o Gastrointestinal: Nausea, Vomiting, Abdominal pain, Constipation, Anorexia
 - Neurological / Psychiatric: Fatigue, Irritability, Confusion, somnolence, Coma
 - Renal: Polyuria, dehydration
 - Others: Bone pain, itch.

Syndromic management of adverse events adapted from (1)

Side effect	Study drug most likely to be	TB drug most likely to be	Perform liver function	Perform serum ionised	Management		
	responsible	responsible	tests	calcium			
					Hypercalcaemia	Abnormal LFTs identified	No biochem. abnormality
Minor							
Mild to moderate anorexia, nausea, abdominal pain, bloating	Either L-arginine or vitamin D	Rifampicin > isoniazid	Yes	Yes	Withdraw patient from study, manage hypercalcaemia in standard fashion ¹	Follow standard protocol (monitor closely; consider H and R cessation if LFT elevation >5x normal)	Advise taking medications with meals
Mild to moderate diarrhoea	arginine	Rifampicin > isoniazid	Yes	No		As above	No change required unless diarrhoea is severe and persistent
Constipation	vitamin D	none	No	Yes			Standard treatment
Joint pains	neither	pyrazinamide	No	No	Give aspirin or NSAID		
Burning sensation in feet	neither	isoniazid	No	No	Give pyridoxine 50-75mg daily		

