Appendix 6: Adverse Events Management

*Classification of Serious Adverse Events

Serious

- Death
- Life-threatening condition
- Hospitalisation

Unexpected

The following are NOT unexpected, they are recognized potential adverse effects:

- Diarrhoea
- Bloating
- Nausea
- Vomiting
- Mild to moderate abdominal pain
- Asymptomatic hypercalcaemia defined as $iCa^{2+} > 1.32 \text{ mmol/L}$
- Symptomatic hypercalcaemia i.e. $iCa^{2+} > 1.32 \text{ mmol/L}$ with one or more of the following symptoms or signs:
 - o Gastrointestinal: Nausea, Vomiting, Abdominal pain, Constipation, Anorexia
 - o Neurological / Psychiatric: Fatigue, Irritability, Confusion, somnolence, Coma
 - Renal: Polyuria, dehydration
 - Others: Bone pain, itch.

Related to study drug

Unrelated

Adverse event is clearly due to extraneous causes (e.g., underlying disease, environment) **Unlikely (must have 2)**

Does not have temporal relationship to intervention.

- 1. Could readily have been produced by the subject's clinical state.
- 2. Could have been due to environmental or other interventions.
- 3. Does not follow known pattern of response to intervention.
- 4. Does not reappear or worsen with reintroduction of intervention.

Possible (must have 2)

- 1. Has a reasonable temporal relationship to intervention.
- 2. Could not readily have been produced by the subject's clinical state.
- 3. Could not readily have been due to environmental or other interventions.
- 4. Follows a known pattern of response to intervention.

Probable (must have 3)

- 1. Has a reasonable temporal relationship to intervention.
- 2. Could not readily have been produced by the subject's clinical state or have been due to environmental or other interventions.
- 3. Follows a known pattern of response to intervention.
- 4. Disappears or decreases with reduction in dose or cessation of intervention.

Definite (must have all 4)

1. Has a reasonable temporal relationship to intervention.

2. Could not readily have been produced by the subject's clinical state or have been due to environmental or other interventions.

3. Follows a known pattern of response to intervention.

4. Disappears or decreases with reduction in dose or cessation of intervention and recurs with re-exposure.

Hypercalcaemia in ADAPT patients

[figure not shown]
- Any patient found to have ionized calcium > 1.32 for the first time should have the test repeated.
- If iCa > 1.32 mmol/L at baseline, patient not eligible for enrolment in the study.

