- If iCa > 1.32 mmol/L at any reading during treatment, follow the flow chart below.
- Hospitalization should be avoided where possible (IV saline can be given in the TB clinic or outpatient clinic); requirement for hospitalisiation in severe, symptomatic people will be discussed on a case-by-case basis.

Hypercalcaemia Grade	Ionised calcium	Equivalent total calcium level (=iCax2)
Mild	1.32 – 1.39 mmol/L	2.60 – 2.79 mmol/L
Moderate	1.40 – 1.49 mmol/L	2.80 – 2.99 mmol/L
Severe, potentially symptomatic	1.50 – 2.25 mmol/L	3.00 – 4.49 mmol/L
Very severe	> 2.25 mmol/L	> 4.50 mmol/L

Symptomatic hypercalacaemia will be defined as one or more of the following symptoms or signs occurring in a person with ionised

calcium > 1.5 mmol/L

- 1.1.1.1 Gastrointestinal: Nausea, Vomiting, Abdominal pain, Constipation, Anorexia
- 1.1.1.2 Neurological / Psychiatric: Fatigue, Irritability, Confusion, somnolence, Coma
- 1.1.1.3 Renal: Polyuria, dehydration
- 1.1.1.4 Others: Bone pain, itch.

Adverse Events Reporting Form

(Non-Serious)

[figure not shown]

If any adverse experiences (including intercurrent illnesses) occurred between this visit and the previous visit, complete this page including your signature. If no adverse experiences occurred, check "None". Sign and date this page at lower right.

None 🗌

Description of Event Onset Date	Onset Date	End Date	Ongoing?	Duration	Туре	Severity	Was the vent serious?	Relationship to Study Drug*	Effect on Test Drug	Outcome of Event	Treatment Required
If the event can be defined as a syndrome rather than a grouping of individual symptoms, please list as a syndrome.	dd/mm/yy	dd/mm/yy	0 = No 1 = Yes	Complete only if duration is less than 24 hours	1 = Single Occurrence 2 = Intermittent 3 = Continuous	1 = Mild 2 = Moderate 3 = Severe	0 = No 1 = Yes	0 = None (disease related) 1 = None (intercurrent illness) 2 = Unlikely (remote) 3 = Possible 4 = Probable 5 = Related	0 = None 1 = Reduced 2 = Interrupted 3 = Discontinued	0 = Recovered 1 = Improved with residual effects 2 = Remained the same 3 = Worsened 4 = Unknown	0 = None 1 = Medication 2 = Hospitalisation 3 = Other

Complete the Serious Adverse Experience / Withdrawal Report Form and notify [Sponsor] immediately. 2Enter in the Concomitant Medications Form

BALKIL HUSP	Serious Adverse Events Reporting Form
Report Date:	Report Type: Initial E Follow-up
Study Drug(s):	UNKOWN: Blinded study Investigator Name:
Site:	TB Clinic RSMM Puskesmas

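### Section 6.3 limits serious adverse events to death and hypercalcaemia, against the any-cause definitions in Appendices 5 and 6, so it is unclear which non-fatal events must reach the DSMC

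*Protocol*

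**What the plan says.** Protocol section 6.3 (Stopping rules) states: "Adverse events defined as serious will be i) death and ii) ionised hypercalemia >1.6 mmol/L or hypercalcaemia requiring hospitalisation". The next sentence reads: "All serious adverse events (SAE) will be reported to the chair of the DSMC". The same section plans interim analyses after 25% and 50% of participants have reached two months, and lets the DSMC request a further one after a study-drug-related SAE.

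Appendix 5 defines an SAE as an untoward occurrence that is "life-threatening, results in death, requires hospitalisation or prolongation of existing hospitalisation, results in significant disability", and it adds congenital anomaly. The event need not be related to any drug. Staff are told: "FILL IN SERIOUS ADVERSE EVENTS REPOTING FORM and record on patient's weekly data collection form and medical file". They then report to named staff by a flowchart.

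Appendix 6 has a three-item list of what is serious: death, "Life-threatening condition" and hospitalisation, with no limit on cause. The SAE form in the same appendix offers wider tick-boxes: fatal, life-threatening, hospital stay caused or prolonged, disability, birth defect, and intervention to prevent another listed outcome.

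Section 9.5 separately requires serious adverse effects to be reported at once to the principal investigators and the DSMC chair, without defining *serious*. Section 9.6 lets the DSMC stop the study for severe events attributable to the study drugs.

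On calcium, Appendix 5 and the first list in Appendix 6 call hypercalcaemia symptomatic when ionised calcium is above 1.32 mmol/L with at least one listed symptom or sign. Below the grading table, Appendix 6 defines it again: "Symptomatic hypercalacaemia will be defined as one or more of the following symptoms or signs occurring in a person with ionised" calcium above 1.5 mmol/L.

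**The concern.** The definition in section 6.3 comes immediately before the DSMC reporting duty and stands in the section that governs early stopping, so it is the natural one to apply to both. Its only non-fatal criteria are calcium criteria. Gastrointestinal events and urticarial rash, which Appendix 5 lists for arginine, would not be serious under 6.3 even if they led to admission, unless the patient died or also met a calcium criterion.

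Safety is the first secondary outcome and part of both trial hypotheses. If staff apply 6.3, the DSMC chair is not notified of a class of events that Appendix 5 and the SAE form treat as serious. If they apply the appendices, the chair is notified. The SAE count by arm, and the DSMC's ground for asking for an extra analysis, would then depend on the page used. The two cut-offs for symptomatic hypercalcaemia create the same problem for a safety table.

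**Working it through.** The plan states no figure to reproduce. The check applies the four statements of seriousness to the same hypothetical events, then follows the reporting routes.

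**1. Same event, four definitions**

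| Event | 6.3 | Appendix 5 | Appendix 6 list | SAE form |
|---|---|---|---|---|
| Death | serious | serious | serious | serious |
| Non-fatal admission for severe diarrhoea, normal calcium | not serious | serious | serious | serious |
| Life-threatening allergic reaction, no admission, normal calcium | not serious | serious | serious | serious |
| Lasting disability, no admission, not life-threatening | not serious | serious | not serious | serious |
| Ionised calcium 1.7 mmol/L, no symptoms, no admission, no intervention | serious | not serious on that ground | not serious on that ground | not serious on that ground |

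Only death gets the same answer in every column. Rows two to four show that 6.3 is narrower than Appendix 5 and the form. Row four shows that the Appendix 6 list is itself shorter than Appendix 5. Row five shows that 6.3 is not simply a subset, because it makes a laboratory value serious on its own.

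The second row is realistic. The side-effect table in Appendix 5 lists severe diarrhoea as a major event with arginine as the likely study drug, and a footnote covers severe gastrointestinal upset attributed to arginine.

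**2. Does that admission have to reach the DSMC?**

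- Under 6.3: no, because it is not an SAE there.
- Under 9.5: yes if *serious* has its Appendix 5 or 6 meaning, no if it has its 6.3 meaning. Section 9.5 does not choose. Its references to Appendices 5 and 6 concern presumed TB-drug side effects, not the SAE definition.
- Under Appendix 5: an SAE form is completed and named staff are told. Any onward step to the DSMC may be in the flowchart, which is not in the text available for review.

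**3. Who is affected?** The gap is defined by the type of event, not by the arm. A non-fatal event without hypercalcaemia falls outside 6.3 in all four arms, 4 × 111 = 444 participants. Arginine is allocated in two arms, 2 × 111 = 222, but those participants are still covered by 6.3 for death and for qualifying hypercalcaemia.

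**4. Symptomatic hypercalcaemia.** The two cut-offs are above 1.32 and above 1.5 mmol/L. Between them lies a band of 1.50 − 1.32 = 0.18 mmol/L, which spans the mild (1.32 to 1.39) and moderate (1.40 to 1.49) grades of the Appendix 6 table. A patient with nausea and ionised calcium of 1.40 mmol/L has symptomatic hypercalcaemia in Appendix 5 and the first Appendix 6 list, but not under the later Appendix 6 definition.

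**The case against.** The strongest reply is section 9.5, which has its own duty to inform the DSMC chair and does not repeat the 6.3 limit. Section 9.6 assumes that the DSMC learns of severe events attributable to either study drug. The DSMC may also see unblinded data (section 7), has two planned interim analyses, and can recommend stopping enrolment on any evidence of harm. The form that staff complete already has the wide categories.

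Much of this stands, and it limits what can be claimed:

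- A reader might infer that no non-fatal serious event on arginine would have to reach the DSMC. That follows only if 6.3 is read alone. With 9.5, the duty is unclear, not absent, and the reporting flowchart cannot be checked.
- A reader might infer that the rule is lopsided against arginine. The only drug-specific non-fatal criterion in 6.3 does concern the toxicity expected of vitamin D, but the omitted events are omitted in every arm, vitamin D and placebo included.
- Appendix 6 says: "Hospitalization should be avoided where possible (IV saline can be given in the TB clinic or outpatient clinic". This might be read as removing the hospitalisation criterion of 6.3. It does not, because the same sentence leaves admission of severe, symptomatic patients to case-by-case discussion.
- The severe grade of 1.50 to 2.25 mmol/L might be read as contradicting the 6.3 criterion of 1.6. A laboratory grade and a reporting criterion are different things, and the adverse event form records severity and seriousness in separate columns. The mismatch is untidy but is not in itself a contradiction.

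The reply does not settle which definition governs. Section 9.5 leaves *serious* undefined, 6.3 is the only definition in the body of the protocol, and section 9.6 uses a different word, severe.

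**Conclusion.** Wrong as written. Section 6.3 contradicts Appendix 5, the Appendix 6 list and the SAE form on what is serious, and 9.5 does not resolve it. Whether non-fatal serious events without hypercalcaemia must be reported to the DSMC chair, and can support a request for an extra interim analysis as SAEs, depends on the page followed. The uncertainty applies to all 444 participants. Its practical size cannot be given as a count, because the documents give no expected rate of such events.

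Appendix 6 also contradicts itself and Appendix 5 on symptomatic hypercalcaemia, over a band of 0.18 mmol/L.

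The conclusion assumes that the flowchart absent from the available text does not state which definition governs DSMC reporting. If it does, practice may be clear, but 6.3 would still need correcting to agree with it.

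**What to change.** Use one SAE definition throughout. The any-cause definition in Appendix 5, which the SAE form largely matches, is the obvious choice. Put it or a reference to it in 6.3, 9.5 and the Appendix 6 list, and state that it governs both reporting to the DSMC chair and the 6.3 trigger for an extra interim analysis. Align the wording in 9.6 with it.

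Reconcile the calcium cut-offs in 6.3 and Appendices 5 and 6 into one definition for counting events. The sponsor should decide the value, and should say whether a calcium result alone is reportable to the DSMC, since the Appendix 5 definition does not by itself cover that case.

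The cost is protocol wording and some additional SAE reports to the DSMC chair. The SAE form already carries the wider categories.
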